#### 2.1 Primary Objective

This is a Pilot Study designed to support future expanded Pivotal Studies of the device. The study is designed to assess arrhythmic events using the implantable cardiac monitor, Biomonitor 3, in subjects presenting to the clinic with TTR-wt cardiac amyloidosis.

#### 2.2 Secondary Objective

The secondary goal is to assess arrhythmogenesis in relation to stage of cardiac amyloidosis

## 3 Study Design

#### 3.1 General Design

This is a pilot study of 50 patients to monitor arrhythmogensis for six months with +31 days post implantation in patients TTR-wt cardiac amyloidosis proven by endomyocardial biopsy or technetium pyrophosphate scintigraphy. Study staff will provide continuous monitoring of the ILR.

The general design is outlined below:

#### 3.2 Primary Study Endpoints

1. Sudden cardiac death (including resuscitated cardiac arrest).

2. Syncope due to heart block or sinus node dysfunction requiring pacemaker

#### 3.3 Secondary Study Endpoints

- 1. All-cause mortality: with a focus on HF deaths and bradycardia/PEA
- 2. PPM implantation and indication, frequent of pacing required, and if BIV pacing is needed
- 3. ICD implantation and indication, frequency of shocks and if appropriate vs inappropriate and if successful defibrillation occurred
- 4. Frequency of NSVT and predictability with other ventricular arrhythmias and sudden cardiac death
- 5. Frequency of atrial flutter or fibrillation and predictability with other arrhythmias including predictability of ventricular arrhythmias and sudden cardiac death

## 4 Subject Selection, Enrollment and Withdrawal

The target population is patients with TTR-wt cardiac amyloidosis. We plan to enroll 50 patients in this pilot study. Specifically, we will enroll 25 patients diagnosed with stage I or stage II disease and 25 with stage III disease.

Patients will be screened and recruited from the Amyloidosis Clinics, heart failure clinics and respective hospital services.

#### 4.1 Inclusion Criteria

- 1. Cardiac biopsy or technetium pyrophosphate scintigraphy confirmed patients
- 2. Stage I, II, and early and late stage III in numbers as described, irrespective of EF or NYHA functional class
- 3. Patients aged 18 -85, both genders and of all races and ethnicities.
- 4. Patients must be competent to give informed consent.
- 5. Patients must be able to have the Biomonitor 3 implanted.
- 6. Amyloid stages I-III patients with existing implantable cardiac devices such as pacemakers or defibrillators

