## 2 Study Objectives

Listed below are the specific aims/objectives for this study.

**Specific Aim 1**: Burden of conduction system disease and arrhythmias, specifically sinus node dysfunction, high grade heart block, and AF and VA, which will identify those who might benefit from a PPM or ICD

**Specific Aim 2**: Mechanism of SCD (asystole, pulseless electrical activity, or sustained VA) and whether this is different in early vs. late stage amyloidosis.

**Specific Aim 3**: Risk factors for SCA and more specifically whether bradycardia or VA predict SCD, or whether there are imaging or clinical characteristics that predict SCA **Specific Aim 4**: Utility of long term ECG monitoring in TTR-wt cardiomyopathy

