## 5 Study Procedures

Arrhythmias will be assessed via home monitoring through the Biomonitor 3 device. Superventricular tachycardia (SVT), ventricular arrhythmias (VA), bradycardia (<35bpm), heart block and atrial arrhythmias are considered of interest.

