#### **Primary Hypothesis:**

The primary hypothesis that arrhythmogenesis and SCD risk in this population is influenced by amyloid cardiomyopathy stage rather than reduced left ventricular ejection fraction, which is often a marker of late disease and increased mortality due to heart failure, and that SCD due to asystole, rather than VA which could be treated with ICD. Conduction system disease causing heart block, atrial arrhythmias and VA leading to SCD may occur earlier in the disease process and treatment of AF, VA, and heart block could improve both morbidity and mortality.

A Student's t-test will be used to compare differences in arrhythmia burden between the patients in the two groups (early stage I-II vs stage III either with any implanted cardiac device).

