#### 6.3 Subject Population(s) for Analysis

All-implanted population: Any subject enrolled into the study and had a device implanted.

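### Patients who already have a pacing-capable device at entry are pooled into the bradycardic burden and pacemaker results, with no at-risk denominator or coding rule

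*Combined protocol and SAP*

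**What the plan says.** Inclusion criterion 6 in Section 4.1 admits "Amyloid stages I-III patients with existing implantable cardiac devices such as pacemakers or defibrillators". Section 4 sets the quota: "we will enroll 25 patients diagnosed with stage I or stage II disease and 25 with stage III disease". There is no cap or separate quota for patients with a device.

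Aim 1 in Section 2 is the "Burden of conduction system disease and arrhythmias, specifically sinus node dysfunction, high grade heart block, and AF and VA". Section 5 states that "bradycardia (<35bpm), heart block and atrial arrhythmias are considered of interest". Primary endpoint 2 (Section 3.2) is "Syncope due to heart block or sinus node dysfunction requiring pacemaker". Secondary endpoint 2 (Section 3.3) is "PPM implantation and indication, frequent of pacing required, and if BIV pacing is needed".

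The only between-group test is a Student's t-test in Section 6.2 (Primary Hypothesis), with this stated purpose: "compare differences in arrhythmia burden between the patients in the two groups (early stage I-II vs stage III either with any implanted cardiac device". The only analysis population, in Section 6.3, is "Any subject enrolled into the study and had a device implanted". Section 6.2 (Descriptive Statistics) also hopes to find baseline characteristics linked to bradycardia that leads to a pacemaker.

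Section 5 has patients with existing devices interrogated at enrollment and at six months. Its paragraph on taking rhythm data from the patient's own device, possibly retrospectively, mentions stage III only.

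**The concern.** Pacing is meant to prevent the slow rates and pauses that the study wants to count. A patient with a working pacing device at entry will contribute few or no recorded episodes below 35 bpm, heart-block pauses or asystole. That patient also essentially cannot reach an endpoint defined by needing a pacemaker. These patients still count in the denominators.

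The result does not fit either reading of Aim 1. If burden means events during the six months, these patients are not at risk and dilute the rate. If burden means all conduction disease in this population, a patient paced for conduction disease is already a case and should add to the count.

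Two results are at stake. One is the overall bradycardic burden and the endpoint 2 frequency, which Section 6.1 intends as a basis for larger trials. The other is the stage comparison of bradycardic burden, which shifts if devices are more common in one stage group.

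**Working it through.** **What can be reproduced.** The plan's only figure here is the sample size, 25 + 25 = 50, which agrees. No power or precision calculation, event rate or device prevalence is given. Everything below is therefore illustration.

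**Assumptions (none from the documents).** Risk r = 0.20 of a bradycardic event in unpaced patients; m of 50 patients paced at entry; no recorded events in paced patients, which is the limiting case. The last column also assumes that every entry device was placed for conduction disease, so it is an upper limit.

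**Overall frequency.** Events E = r × (50 − m). Pooled rate = E/50. At-risk rate = E/(50 − m). Prevalent plus incident = (E + m)/50.

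| Paced at entry | Pooled | At risk | Prevalent plus incident (up to) |
|---|---|---|---|
| 5 | 9/50 = 18% | 9/45 = 20% | 14/50 = 28% |
| 10 | 8/50 = 16% | 8/40 = 20% | 18/50 = 36% |
| 15 | 7/50 = 14% | 7/35 = 20% | 22/50 = 44% |
| 20 | 6/50 = 12% | 6/30 = 20% | 26/50 = 52% |

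Exact (Clopper-Pearson) 95% intervals with 10 paced: pooled 7.2-29.1%, at risk 9.1-35.6%, prevalent plus incident 22.9-50.8%. The pooled figure matches neither of the other two, although at this sample size the pooled and at-risk intervals overlap heavily.

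**Stage comparison.** Let p be the share paced in each group. With no recorded bradycardic burden in paced patients:

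observed ratio III / I-II = ratio among unpaced patients × (1 − p_III) / (1 − p_I-II)

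If the ratio among unpaced patients is 1:

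| Paced, I-II / III | Observed ratio |
|---|---|
| 20% / 20% | 0.80/0.80 = 1.00 |
| 10% / 30% | 0.70/0.90 = 0.78 |
| 0% / 40% | 0.60/1.00 = 0.60 |
| 30% / 10% | 0.90/0.70 = 1.29 |

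At 10%/30%, a ratio of 1.5 among unpaced patients would appear as 1.5 × 0.778 = 1.17, and a ratio of 1/0.778 = 1.29 would vanish. With equal prevalence the ratio is unchanged. The distortion therefore depends on an imbalance that the documents neither report nor rule out, and it can go either way.

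**The sections side by side.** Section 4.1 item 6 covers stages I-III, and the interrogation schedule in Section 5 covers all patients with existing devices. The own-device monitoring paragraph in Section 5 names stage III only. Section 6.2 includes any implanted cardiac device. Section 6.3 does not say which device. If it means any cardiac device, all these patients are in the population. If it means the Biomonitor 3, patients followed only through their own device leave the sole population although Section 6.2 includes them. A paced patient who also received a Biomonitor 3 would stay in. Neither reading supplies an at-risk set.

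**The case against.** The strongest reply is that the plan already collects what is needed. Section 3.3 makes pacemaker indication and pacing frequency a secondary endpoint, Section 5 schedules interrogations, and Section 6.2 tabulates baseline values of the outcome variables by group. Read generously, that could show entry devices by stage. This stands in part: the data should be available, but no denominator or coding rule follows from them.

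A reader might infer that the plan scores paced patients as zero. It does not. The unit and coding of arrhythmia burden are not defined for any patient. The supportable statement is that these patients are pooled with no coding given, while pacing suppresses what their recordings can show.

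A reader might also infer that a stage test of endpoint 2 or of pacemaker implantation is biased. Section 6.2 plans no such test; the t-test is on burden. Nor is a comparison limited to unpaced patients the true population burden that Section 6.1 seeks. It leaves out patients whose conduction disease was already treated, perhaps unequally by stage.

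Finally, every magnitude is assumed, and this is a pilot of 50. That is fair. At an assumed 5% risk with 10 paced, the contrast is only 2/50 = 4% against 2/40 = 5%. Sampling error exceeds the shift within this study, but a later trial that reuses the pooled rate inherits the wrong denominator.

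Section 4.4.1 does not answer the point. It concerns devices received during the study, and only how those patients are then monitored.

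**Conclusion.** The point holds and should be fixed before analysis. Following Sections 4.1, 6.2 and 6.3 as written mixes patients already paced at entry into the bradycardic burden comparison and the endpoint 2 denominator. The resulting figures estimate neither incident events among those at risk nor total conduction disease. The search in Section 6.2 for predictors of bradycardia leading to a pacemaker has the same gap.

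The conclusion rests on general reasoning that pacing masks slow rhythms. Zero events in paced patients is only the limiting case. It does not extend to AF or VA, which remain observable. Size and direction are unknown without device prevalence by stage; the 16%, 20% and 36% figures are illustrative.

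**What to change.** 1. In Section 6.3, add an at-risk set of patients with no pacing-capable device at entry. Use it for primary endpoint 2, new pacemaker implantation, and the burden of bradycardia, heart block and asystole. Count bradycardic burden only up to any pacing device implanted during follow-up, because the same masking begins then.
2. Tabulate devices present at entry by stage, with indication and pacing frequency. Count those placed for conduction disease as prevalent conduction disease.
3. Keep the all-patient analysis alongside.
4. State that the at-risk result applies to unpaced patients only.
5. Reconcile Sections 4.1, 5, 6.2 and 6.3 on which stages the existing-device pathway covers and which device the Section 6.3 population refers to.

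The cost is SAP wording. Device status should be available from the enrollment interrogation, so no new visit is needed. The price is smaller denominators and a selected population. At an observed 20%, the exact 95% interval for one stage group widens from 6.8-40.7% (5/25) to 4.3-48.1% (3/15). The entry-device table and the all-patient analysis keep the excluded patients visible.

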#### 4.2 Exclusion Criteria

- 1. Significant coronary artery disease > 75% luminal stenosis in at least 1 epicardial vessel (by cardiac catheterization or coronary computed tomography), or history of myocardial infarction or coronary revascularization.
- 2. Congenital heart disease.
- 3. Pregnant patients
- 4. Patients whose heart failure is felt to be secondary to primary valvular disease (≥ moderate/severe mitral regurgitation), uncorrected thyroid disease, obstructive or hypertrophic cardiomyopathy, pericardial disease or a systemic illness.
- 5. Absolute contraindications to cardiac MRI (such as renal failure with GFR<30%).
- 6. Unwilling or unable to provide informed consent.
- 7. Patients with other life threatening diseases that would likely decrease their life expectancy over the next four years.
- 8. Patients who are post cardiac transplant.
- 9. Difficulty to attend the follow-up schedule due to a history of medical noncompliance, difficulty, or unwillingness to return to the study center for follow up.
- 10. Evidence of ongoing bacteremia or sepsis preventing implantation of a device.
- 11. Unwilling or able to have the Biomonitor 3 interrogated

#### 4.3 Subject Recruitment, Enrollment and Screening

Subjects will be screened and recruited from the from the Amyloidosis Clinics, heart failure clinics and respective hospital services. Patients will receive standard of care therapy including staging with cardiac biomarkers. We will recruit 25 patients with stage I or II and 25 patients with stage III. Prior to time of recruitment, inclusion and exclusion criteria will be reviewed for each patient.

There are no known contraindications for the insertion of the BioMonitor 3. However, the patient's particular medical condition may dictate whether or not a subcutaneous, chronically inserted device can be tolerated.

Patients will have the option to leave the device in situ for the lifetime of the device. If opting for the full battery lifetime, the patient/insurance company would be responsible for the continued monitoring after the 6 month study period and the explanation of the device at battery end of life.

#### 4.4 Early Withdrawal of Subjects

#### 4.4.1 When and How to Withdraw Subjects

Patients may withdraw at any time from the study. Reason for withdraw may include but are not limited to adverse events, progression of disease requiring withdrawal or simply the patient's decision to withdraw.

If a subject does withdraw, that subject will be replaced according to the originally assigned group to permit enrollment of 50 patients complete the study.

Patients may be withdrawn from the study by the investigators if an insertable monitor requires emergent removal. Reasons for removal include, but are not limited to: patient death; loss of sensing; inability to program/interrogate the inserted monitor; infection, battery end of life (normal or premature); system upgrade; physician preference for another insertable monitor model; and/or other reason(s) which may or may not be known to the insertable monitor manufacturer. Complications related to other portions of the insertable monitor system (i.e., patient) may also result in insertable monitor removal. The table below summarizes some of the more common reasons for insertable monitor removal.

Source	Cause	Possible Effect
Battery	Premature depletion or other cause(s) resulting in excessive battery current drain.	Inability to program/interrogate; sensing difficulty.
Circuitry	Electrical parameter changes due to shorts, opens, or component parametric drift Electromagnetic Interference (EMI) from large power tools, industrial equipment, electrocautery, defibrillation, radiation therapy, RF ablation therapy, etc.	Reversion to "Elective Replacement" or electrical reset parameters; inability to program/ interrogate; other damage to circuit components resulting in permanent or temporary parameter changes.
Patient	Normal medical complication	Infection
	Body rejection phenomena	Fluid accumulation; migration; erosion.
	Physician preference	Upgrade to an implantable cardiac pacemaker or implantable cardioverter defibrillator.

If the device is removed due to need for a pacemaker or implantable cardioverter defibrillator the patient will continue to be monitored via the pacemaker or defibrillator as per clinically indicated standard of care monitoring protocol and intervals.

If a subject chooses to withdraw from the study, and requests the monitor to be explanted prior to the end of the 6 month study monitoring period, there will be no further follow up.

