#### 4.4.2 Data Collection and Follow-up for Withdrawn Subjects

Even though a subject has withdrawn from the study, follow-up and survival data on such subjects throughout the protocol defined follow-up period will still need to be collected if possible. Such data is important to the integrity of the final study analysis since early withdrawal could be related to the safety profile of the study device. If a subject withdraws consent to participate in the study, for subject safety reasons, attempts will be made to obtain permission to collect follow up information whenever possible.

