#### **Post-study Adverse Event**

All unresolved adverse events will be followed by the investigator until the events are resolved, the subject is lost to follow-up, or the adverse event is otherwise explained. At the last scheduled visit, the investigator will instruct each subject to report any subsequent event(s) that the subject, or the subject's personal physician, believes might reasonably be related to participation in this study. The investigator will notify the study regulatory sponsor of any death or adverse event occurring at any time after a subject has discontinued or terminated study participation that may reasonably be related to this study. The sponsor should also be notified if the investigator is aware of the development of problems, cancer or of a congenital anomaly in a subsequently conceived offspring of a subject that has participated in this study.

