#### **Adverse Event Reporting Period**

1. Patients will be monitored for 6 months and all adverse events withing the 6 month time frame will be recorded. If patients choose to retain the monitor, all subsequent monitoring will be clinically indicated.

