#### 7.2 Recording of Adverse Events

Study subjects will be routinely questioned about adverse effects at study visits. Information on all adverse events will be recorded immediately in the source document, and also in the appropriate adverse event section of the case report form (CRF). All clearly related signs, symptoms, and abnormal physical exam of the implant site will be recorded in the source document.

All adverse events occurring during the study period will be recorded. All observed or volunteered adverse effects (serious or non-serious) will be recorded in the subjects' case history. For all adverse effects sufficient information will be pursued and or obtained as to permit; an adequate determination of the outcome, an assessment of the casual relationship between the adverse effect and the device. The clinical course of each event will be followed until resolution, stabilization, or until it has been ultimately determined that the study treatment or participation is not the probable cause.

The only laboratory values that will prompt an investigation would be an elevated leukocytosis IN ADDITION to a physical inspection of the implanted site. If the implanted site is erythematous, hot, swollen, or there is drainage from the skin would further steps need to be taken to possibly extract the device. Positive blood cultures would indicate the necessity of a physical exam and inspection of the implant site.

A form will be created for capturing information related to adverse events and submitted to the IRB.

Adverse Event CRF:

- Subject Study Number/Identifier
- Device information (model and serial number)
- Date of event onset
- Description of the event
- Indicate if device needed to be explanted
- Subject current status, or if the event was resolved
- Principal Investigator assessment of if the event was serious and justification for

determination

• Principal Investigator assessment of causality and relationship to study treatment.

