## 8 Data Handling and Record Keeping

#### 8.1 Confidentiality

Information about study subjects will be kept confidential and managed according to the requirements of the Health Insurance Portability and Accountability Act of 1996 (HIPAA). Those regulations require a signed subject authorization informing the subject of the following:

- What protected health information (PHI) will be collected from subjects in this study
- Who will have access to that information and why
- Who will use or disclose that information
- The rights of a research subject to revoke their authorization for use of their PHI.

(This information is contained within the Mayo IRB Informed Consent Template Section 12) In the event that a subject revokes authorization to collect or use PHI, the investigator, by regulation, retains the ability to use all information collected prior to the revocation of subject authorization. For subjects that have revoked authorization to collect or use PHI, attempts should be made to obtain permission to collect at least vital status (long term survival status that the subject is alive) at the end of their scheduled study period.

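### Section 4.4.1 ends follow-up for subjects who withdraw and ask for early explant, while Section 4.4.2 still wants their follow-up and survival data

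*Combined protocol and SAP*

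**What the plan says.** Section 4.4.1 covers several routes out of the study. For a subject who chooses to withdraw, it says that if the subject "requests the monitor to be explanted prior to the end of the 6 month study monitoring period, there will be no further follow up". Removal at the investigator's decision, for example for infection or loss of sensing, is in a separate paragraph that has no such sentence.

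Section 4.4.2 sets the rule for data collection after withdrawal: "follow-up and survival data on such subjects throughout the protocol defined follow-up period will still need to be collected if possible". Its reason is that "early withdrawal could be related to the safety profile of the study device". Where consent is withdrawn, it has staff seek permission to go on collecting information.

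Three parts of Section 7 also bear on these subjects:

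- Adverse Event Reporting Period: "all adverse events withing the 6 month time frame will be recorded".
- Section 7.2: "The clinical course of each event will be followed until resolution, stabilization", or until the study is judged not to be the probable cause.
- Post-study Adverse Event: "All unresolved adverse events will be followed by the investigator until the events are resolved", with loss to follow-up or another explanation as the other end points. The investigator must also notify the sponsor of "any death or adverse event occurring at any time after a subject has discontinued or terminated study participation" if it may reasonably be related to the study.

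Section 8.1 adds that when authorization to use health information is revoked, "attempts should be made to obtain permission to collect at least vital status".

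**The concern.** Two adjacent subsections give different instructions for the same subject. One rules out further follow-up; the other requires an attempt at it. Section 4.4.1 names adverse events first among the reasons for withdrawing, so a subject who asks for the device to be taken out may have an open event.

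The outcomes at stake are study endpoints: sudden cardiac death and syncope leading to a pacemaker (Section 3.2), and all-cause mortality and pacemaker or defibrillator implantation (Section 3.3). Section 6.3 keeps every implanted subject in the analysis population. Under the literal reading, these subjects enter the denominators with unknown outcomes after explant. The loss is also tied to device removal, so it cannot be assumed to be unrelated to device safety. The only provision for missing data, in Section 6.2, is a query of the medical record at the end of the study. It does not say whether the records of these subjects may be queried.

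**Working it through.** **The texts side by side**

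| Place | Who is covered | What is required | What ends it |
|---|---|---|---|
| 4.4.1 | Subjects who choose to leave and request explant before month 6 | No follow-up | Explant |
| 4.4.2 | All withdrawn subjects | Follow-up and survival data, if possible | End of the follow-up period |
| Adverse Event Reporting Period | All patients | Recording of adverse events | Month 6 |
| 7.2 | Every adverse event | Follow-up of its course | Resolution, stabilization, or study judged not the probable cause |
| Post-study Adverse Event | Unresolved events | Follow-up by the investigator | Resolution, loss to follow-up, or another explanation |
| 8.1 | Subjects who revoke authorization | Attempt to get permission for vital status | End of the scheduled study period |

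The first row is a subset of the second, and the two requirements are opposed. Qualifying 4.4.2 by what is possible does not remove the conflict: it still calls for an attempt. The Section 7 rows are in tension with the first row but not in flat contradiction, because some of them allow an event to be closed without resolution.

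**Size**

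The plan has no figure to reproduce: it states no early-explant rate and no expected number of events. What follows is an illustration.

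Inputs from the documents:
- Four-year survival of 57%, 42% and 18% in stages I, II and III (Section 1.4.1).
- 25 patients in stage I or II and 25 in stage III (Section 4).
- Six months of monitoring.

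Assumptions:
- A constant hazard.
- 5%, 10% or 20% of 50 patients leave with explant at month 3 (2.5, 5 or 10 patients), split evenly between the two groups.
- Nothing is learned about them afterwards.

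Six-month cumulative hazard, H = -ln(S)/8:
- Stage I: -ln(0.57)/8 = 0.070
- Stage II: -ln(0.42)/8 = 0.108
- Stage III: -ln(0.18)/8 = 0.214

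Mortality in months 3 to 6 for a patient alive at month 3, 1 - exp(-H/2): 3.5%, 5.3% and 10.2%.

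Missed deaths at 10% leaving, taking the early-stage group as all stage I and then all stage II:
- 2.5 × 0.035 + 2.5 × 0.102 = 0.34
- 2.5 × 0.053 + 2.5 × 0.102 = 0.39

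| Scenario | 5% leave | 10% leave | 20% leave |
|---|---|---|---|
| Explant at month 3, even split | 0.17-0.19 | 0.34-0.39 | 0.68-0.77 |
| Same, half the hazard | 0.09-0.10 | 0.17-0.20 | 0.35-0.39 |
| Explant at month 3, all leavers stage III | 0.25 | 0.51 | 1.02 |
| Explant at month 1, even split | 0.28-0.31 | 0.55-0.62 | 1.10-1.25 |

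For month 1 the remaining mortality is 1 - exp(-5H/6): 5.7%, 8.6% and 16.4%.

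Deaths expected in 50 patients over six months, with 1 - exp(-H) = 6.8%, 10.3% and 19.3%: 25 × (0.068 to 0.103) + 25 × 0.193 = 6.5 to 7.4. At half the hazard this is 3.4 to 3.9.

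Some patients are followed through an existing pacemaker or defibrillator (Sections 4.1 and 5). If only 40 or 30 carry the study monitor, 10% leaving at month 3 gives 0.27-0.31 or 0.20-0.23 missed deaths.

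**Worst case for any yes/no endpoint**

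The documents give no six-month rates for the primary endpoints, so a bound is the most that can be offered. If 50 implanted patients complete and k more leave with unknown outcomes, the gap between counting all k as events and none is k/(50+k): 1/51 = 2.0, 5/55 = 9.1 and 10/60 = 16.7 percentage points for k = 1, 5 and 10. These are limits, not expected errors.

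**The case against.** The best defence is context. The sentence closes a discussion of monitor removal, straight after a statement that patients upgraded to a pacemaker or defibrillator stay monitored through that device. Read there, it may mean only that device monitoring stops, with 4.4.2 governing data collection. That is plausible, but it is an inference; the sentence is unqualified.

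Four further points limit the concern, and they stand:

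- A reader might infer that anyone who loses the device to a complication goes unfollowed. The documents do not support that: the sentence reaches only those who choose to leave and also request explant.
- A reader might infer that the safety sections flatly contradict 4.4.1. They allow for loss to follow-up, another explanation, or a judgment that the study is not the cause. The text on events after discontinuation is a duty to notify, which can coexist with no active follow-up.
- All patients are treated at one centre whose record is queried at study end, so complete loss of these outcomes is a worst case.
- The mortality figures rest on assumed explant rates and timing and concern a secondary endpoint. Chart review also cannot restore rhythm data lost at explant.

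A reader might also infer that replacing leavers biases the results. No bias can be shown: Section 6.3 keeps replaced subjects who were implanted.

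**Conclusion.** The conflict between 4.4.1 and 4.4.2 is real and should be corrected before staff have to choose between them. The tension with the safety sections is secondary. Under assumed explant rates of 5% to 20%, expected missed deaths are mostly below one. They reach about one only at 20%, with all leavers in stage III or explant at month 1. These figures depend on a constant hazard from the survival cited in the protocol and on no information after explant. The effect is small unless withdrawal is related to outcome, a possibility that 4.4.2 itself raises for device safety. Nothing here shows that the pilot's descriptive results would be materially biased. The case rests on contradictory instructions and on safety and endpoint data that are cheap to keep.

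**What to change.** Reconcile the passages. Limit the 4.4.1 sentence to the end of device monitoring, and state that vital status, syncope, pacemaker or defibrillator implantation and device-related adverse events are collected to month 6 from the medical record. Where consent or authorization is withdrawn, collect these only with the permission that Sections 4.4.2 and 8.1 already say will be sought.

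The cost is a reworded sentence, a little chart review in a record that the study already queries, and a permission request where needed.

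A related clarification could go in the same amendment. Section 4.4.1 lists death and system upgrade among the removal reasons under investigator withdrawal. Yet it keeps upgraded patients under monitoring, and Section 5 reviews the final rhythm of those who die. The sponsor could state whether patients who die or receive a pacemaker or defibrillator count as withdrawn, and whether 50 means enrolled or completed. The documents do not settle whether such patients are replaced, and no rule is proposed here.
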